### 5.2.4 Test-of-cure visit

The following assessments and procedures will be performed at the TOC visit (7–14 days after the last dose of study drug; see Table 3):

- Physical examination (see Section 5.5.2)
- Body weight (see Section 5.5.2)
- Vital signs (including body temperature, respiratory rate, pulse rate, and systolic and diastolic blood pressures) and pulse oximetry (see Section 5.5.3)

- Signs and symptoms of LOS (see Section 5.6.5)
- Local laboratory tests will be performed only if clinically indicated based on the Investigator's judgement in accordance with local standard of care (see Section 5.5.4)
- Imaging tests (e.g., chest X-ray, ultrasound, CT scan, MRI) will be performed if clinically indicated based on the Investigator's judgement in accordance with local standard of care.
- Collection of blood and other specimens for microbiological evaluation as clinically indicated based on the Investigator's judgement in accordance with local standard of care (see Section 5.4).
- Overall clinical outcome assessment: clinical cure, clinical failure, or unevaluable (see Section 5.6.1)
- Microbiological outcome assessment: eradication, presumed eradication, persistence, presumed persistence, or unevaluable (see Section 5.6.3)
- Review and recording of changes in concomitant medications and concomitant procedures
- Adverse events must be monitored and recorded as outlined in Section 7.4.

### 5.2.5 Last follow-up visit

The following assessments and procedures will be performed at the LFU visit (28–35 days after the last dose of study drug; see Table 3). This visit can be done by telephone contact unless an examination is needed to evaluate relapse or abnormalities recorded during the TOC visit.

- Review and recording of changes in concomitant medications and concomitant procedures
- Adverse events must be monitored and recorded as outlined Section 7.4.
- Survival status
- Relapse assessment: Deterioration of the clinical condition compared to the TOC visit, microbiological recurrence, or the requirement for additional antimicrobial therapy for LOS

## 5.3 Medical history and concomitant medications

### 5.3.1 Medical history

A full medical history, including relevant abnormalities, surgeries, diseases, or disorders, must be obtained at Screening.

Medical history also includes any relevant worsening of a patient's condition which occurs after consent, but prior to the start of first study-drug administration (see Section 7.2.1).

### 5.3.2 Prohibited concomitant medications

- Systemic antibacterial therapy other than ampicillin and aminoglycosides

### 5.3.3 Permitted concomitant medications

- Ampicillin and/or an aminoglycoside based on the Investigator's judgement, local standard of care, and/or isolated or presumed pathogens
- Topical antibacterial medications
- Acetaminophen or paracetamol
- Nonsteroidal anti-inflammatory drugs and systemic steroids
- Non-antibacterial standard-of-care medications

### 5.4 Microbiology assessments

Microbiological evaluation and outcome assessment may be based on blood samples, urine, cerebrospinal fluid, or any other suitable specimen samples.

If clinically indicated and performed as part of the patient's regular medical care, blood is to be obtained for microbiological evaluation at the Screening visit/Baseline (if possible before any antibiotics are administered), or at any time through to LFU visit. Cultures should be repeated in accordance with standard of care if a positive result is obtained, until sterilization is confirmed. Gram stain, culture/PCR, and organism identification are to be performed at the local or regional laboratory, as applicable. All isolates, regardless of specimen source, are to be sent to the central microbiology laboratory for final organism identification and study-specific susceptibility testing.

See the Laboratory Manual for procedures regarding the collection, processing, storage, and shipment of pathogens. Rules for the assessment of the validity of pathogens are described in the Statistical Analysis Plan (SAP).

### 5.5 Safety assessments

The Investigator will evaluate safety by AE monitoring, clinical laboratory tests, vital signs, and physical examination (see schedule of assessments; [Table 3](#)).

Safety assessments must be performed at intervals indicated in the schedule of assessments ([Table 3](#)). More frequent assessments may be performed at the Investigator's discretion, if medically indicated.

Safety data will be reviewed by the Sponsor and by the DSMB (see [Section 3.4](#)).

#### 5.5.1 Adverse event monitoring

See [Section 7.4](#) for details regarding AE collection and management.

#### 5.5.2 Physical examination

A complete physical examination will be performed at Screening and at the EOT and TOC visits in accordance with [Table 3](#), and will include examination of general appearance, skin, head, neck, eyes, ears, nose, throat, cardiovascular system, thorax/lungs, abdomen, lymph nodes, extremities, and nervous system.

Complete or targeted physical examinations focusing on changes from baseline will be performed during the active treatment period at the discretion of the Investigator as clinically indicated in accordance with local standard of care.

Any clinically-significant physical change from baseline that occurs after first study-drug

administration must be reported as an AE (see Section [7.4](#)).

A patient's length will be measured only during the Screening visit.

Body weight will be measured at Screening, daily during the active treatment period, and at the EOT and TOC visits. The weight obtained within 12 hours prior to the first dose of study drug will be used to calculate the dose on Day 1. From Day 2 until the last day of study treatment, the dose should be calculated based on the patient's first body weight of the day.

### **5.5.3 Vital signs and pulse oximetry**

Vital signs (including body temperature, respiratory rate, pulse rate, and systolic and diastolic blood pressures) and pulse oximetry must be recorded during all visits from Screening up to and including the TOC visit ([Table 3](#)). During the active treatment period, vital signs must be recorded within 30 minutes before the first study drug administration, and then three times daily; if continuously monitored, the highest body temperature, respiratory rate, and pulse rate, and the lowest systolic and diastolic blood pressures and oxygen saturation obtained during an 8-hour period, will be recorded.

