- 2 EOT assessment is to be performed on the day of last study drug administration, or as a separate visit within 24 hours of last study-drug administration.
- 3 The LFU visit may be performed by telephone contact if the patient has been discharged from the hospital, unless an examination is needed to evaluate relapse or abnormalities recorded during the TOC visit (see Section 5.2.5).
- 4 Written informed consent (or, in the event of an emergency, verbal informed consent followed by written consent as soon as the situation allows) must be obtained before any study-specific procedures or assessments take place (see Section 10.2).
- 5 Prior medications taken within 7 days before the first dose of study drug is to be recorded. For patients who are being breastfed, all medications taken by the lactating mother within 3 days before the first dose of study drug is to be recorded.
- 6 Complete physical examination is to be performed at Screening, the EOT visit, and the TOC visit. Complete or targeted physical examinations focusing on changes from baseline is to be performed during the active treatment period at the discretion of the Investigator as clinically indicated in accordance with local standard of care (see Section 5.5.2).
- 7 Body weight on Day 1, which is to be used for Day 1 dose calculation, should be obtained within 12 hours prior to the first dose of study drug. From Day 2 until the last day of study treatment, the dose should be calculated based on the patient's first body weight of the day (see Section 5.5.2).
- 8 Vital signs (including body temperature, respiratory rate, pulse rate, and systolic and diastolic blood pressures) and pulse oximetry must be recorded within 30 minutes before the first study drug administration, and then three times daily during the active treatment period; if continuously monitored, the highest body temperature, respiratory rate, and pulse rate, and the lowest systolic and diastolic blood pressures and oxygen saturation obtained during an 8-hour period, are to be recorded. Vital signs and pulse oximetry must also be obtained at the EOT and the TOC visits (see Section 5.5.3).

- 9 Hematology, blood chemistry, and urinalysis are to be performed at baseline and at the EOT visit. At all other visits, these laboratory evaluations are to be performed only if clinically indicated based on the Investigator's judgment in accordance with local standard of care (for details, see Sections [5.2.2](#), [5.2.4](#), and [5.5.4](#)).

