### 5.2.2 Active treatment visits

The following assessments and procedures will be performed during study treatment visits (Day 1 to Day 10 [or up to Day 14]; see [Table 3](#)):

- Study drug administration should be initiated as soon as possible after enrollment. Ceftobiprole medocaril will be reconstituted and diluted for IV administration and administered as described in the Pharmacy Manual and in Section [6.6](#). If applicable, ampicillin and/or an aminoglycoside will be prepared and administered according to the manufacturer's instructions and/or local standard of care. The dates and exact start and stop times of all ceftobiprole infusions, and if applicable, of all ampicillin and/or aminoglycoside infusions/injections must be recorded in the eCRF.
- Physical examination: complete or brief physical examinations focusing on changes from baseline during the active treatment period will be performed at the discretion of the Investigator as clinically indicated in accordance with local standard of care (see Section [5.5.2](#))
- Body weight (see Section [5.5.2](#)): body weight on Day 1, which will be used for Day 1 dose calculation, should be obtained within 12 hours prior to the first dose of study drug. From Day 2 until the last day of study treatment, the dose should be calculated based on the patient's first body weight of the day.
- Vital signs (including body temperature, respiratory rate, pulse rate, and systolic and diastolic blood pressures) and pulse oximetry must be recorded within 30 minutes before the first study drug administration, and then three times daily during the active treatment period. If continuously monitored, the highest body temperature, respiratory rate, and pulse rate, and the lowest systolic and diastolic blood pressures and oxygen saturation obtained during an 8-hour period, will be recorded (see Section [5.5.3](#)).
- Signs and symptoms of LOS (see Section [5.6.4](#))
- Local laboratory tests will be performed only if clinically indicated based on the Investigator's judgement in accordance with local standard of care (see Section [5.5.4](#)).
- If clinically indicated, measurement of urine output (over at least an 8-hour period). Use of a urinary catheter is based on the Investigator's judgement in accordance with local standard of care. Urinary catheters are not required for the purposes of this study.

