### **8.4.1 Primary endpoint analysis**

#### **8.4.1.1 Safety/tolerability analysis**

Safety will be assessed through summaries of AEs, clinical laboratory tests, vital signs, and physical examination findings. All safety analyses will be based on the Safety population.

The incidence of AEs and SAEs will be tabulated by System Organ Class (SOC) and Preferred Term (PT), and by severity, relationship to treatment, and outcome. Tables of AEs leading to study drug discontinuation and withdrawal from the study will also be provided.

Adverse occurrences (as defined in Section 7.2) will be provided in a listing.

Descriptive statistics summarising local laboratory data will be presented by study visit. The change from baseline to each post-baseline visit and to the overall worst post-baseline value will also be summarised.

Descriptive statistics of vital signs will be presented by study visit, as well as the change from baseline at each study visit. The percentage of abnormalities in the physical examination will be presented by study visit.

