## 4.3 Other important considerations

### 4.3.1 Definition of baseline

Unless otherwise specified, baseline is defined as the last non-missing assessment prior to the first study drug administration. Both scheduled and unscheduled visits and assessments will be used in determining baseline.

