#### 4.3.3 Study day calculation and visit windows

Visit windowing approaches will not be used for this study, and visit-based summaries will include scheduled assessments only. If more than the specified number of measurements has been taken in a scheduled visit, the latest recorded values will be used in visit summaries, unless otherwise stated. All scheduled and unscheduled post-baseline assessments will be used for derivation of minimum and maximum post-baseline values. If more than one assessment has the same minimum or maximum value, then the record with earliest occurrence will be selected respectively as the minimum or maximum assessment.

The following conventions will be used to calculate analysis study day:

- Day 1 is the day of first study drug administration. Day -1 is the day before Day 1. No Day 0 is defined for this study.
- Prior to Day 1, the algorithm is:  
Study Day = visit/examination date – date of first study drug administration
- For Day 1 and subsequent days, the algorithm is:  
Study Day = visit/examination date – date of first study drug administration + 1.

Summary data such as AEs and concomitant medications will not be reported by visit. Tables that report abnormalities (e.g., clinically-notable abnormalities, laboratory shift tables) will include all assessments.

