#### **9.4 Vital signs**

Summary tables of observed values and changes from baseline, as well as minimum and maximum post-baseline values, will be presented for vital-sign data, including weight (g), body temperature (°C), respiration rate (breaths/minute), pulse rate (bpm), systolic blood pressure (mmHg), diastolic blood pressure (mmHg), and pulse oximetry (%), at each visit on a given timepoint, in the Safety population.

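### SAP 9.4 does not separate one-sided 8-hour vital-sign extremes from single readings, so in continuously monitored infants on-treatment change is shifted and the opposite-side minimum or maximum is unreliable

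*Protocol*

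**What the plan says.** Vital signs are part of the primary safety endpoint (Protocol 8.1.1, SAP 3.2.1). Under Protocol Table 3, footnote 8, they "must be recorded within 30 minutes before the first study drug administration, and then three times daily" during active treatment. The same footnote, Protocol 5.2.2 and Protocol 5.5.3 then give the rule for monitored infants: "if continuously monitored, the highest body temperature, respiratory rate, and pulse rate, and the lowest systolic and diastolic blood pressures and oxygen saturation obtained" over an 8-hour period is what goes into the record. The other side (lowest pulse, highest systolic pressure and so on) is not requested. No 8-hour rule is stated for the TOC visit. EOT may fall on the day of the last dose (Protocol 5.2.3).

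On the analysis side, Protocol 8.4.1.1 promises: "Descriptive statistics of vital signs will be presented by study visit, as well as the change from baseline at each study visit". SAP 4.3.1 sets the reference: "baseline is defined as the last non-missing assessment prior to the first study drug administration". SAP 9.4 states: "Summary tables of observed values and changes from baseline, as well as minimum and maximum post-baseline values, will be presented for vital-sign data", and lists weight, temperature, respiratory rate, pulse, both blood pressures and pulse oximetry. SAP 4.3.3 supplies the derivation: "All scheduled and unscheduled post-baseline assessments will be used for derivation of minimum and maximum post-baseline values". None of these sections distinguishes a single reading from an 8-hour extreme.

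**The concern.** The collection rule is one-sided and the analysis is two-sided. In a monitored infant, the on-treatment pulse record is a series of 8-hour maxima. Taking the smallest of them and labelling it the minimum pulse does not describe how low the pulse went. Subtracting a single pre-dose reading from an 8-hour maximum gives a change that is partly a product of how the infant was observed.

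The trial has one arm, so no comparator carries the same artefact and cancels it. The planned minimum is eight infants, so a few monitored infants can move a pooled row. A reader of the tables could take a mean rise in pulse, a mean fall in blood pressure, or a reassuring minimum pulse as an observation about the drug.

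**Working it through.** The plan states no figure on this point and no power calculation exists, so there is nothing to reproduce. The check sets the sections against each other and asks what the stated rules return when the infant's true level does not change.

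1. **What the record contains.** Three recordings a day and an 8-hour period fit together: 3 × 8 h = 24 h. The natural reading is that, for a monitored infant, the extremes are the content of the three daily recordings. Treatment lasts 3–10 days, extendable to 14, so there are between 3 × 3 = 9 and 3 × 14 = 42 such values per parameter.

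2. **Baseline.** The last assessment before the first dose is normally the one taken in the 30 minutes beforehand, hence a single reading B. The SAP does not say so outright; this is a condition of the argument.

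3. **Change from baseline.** Let X be the vital sign at each monitored moment, with a stable mean μ. Let M be the highest X in an 8-hour period.
   - For pulse, temperature and respiratory rate, M is at least as large as every X in its period, so E(M − B) = E(M) − μ ≥ 0, and it exceeds 0 whenever X varies within the period.
   - For blood pressures and saturation the recorded value is the lowest, L, and E(L − B) = E(L) − μ ≤ 0 by the same reasoning.
   - The sign therefore follows from the rules alone. The size, E(M) − μ, depends on how often the monitor reads, how correlated successive readings are, and how variable the infant is. The documents give none of these.

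4. **Opposite-side extreme.** SAP 4.3.3 returns, for minimum pulse, the smallest of all the M values together with any EOT, TOC and unscheduled values. Each M is at least as large as the lowest X in its own period, so the tabulated minimum cannot lie below the true one and will usually lie above it. They agree only if the true low happens to be one of those other readings, or if a period shows no variation. The mirror argument holds for maximum blood pressure and maximum saturation.

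5. **Collected side.** Maximum pulse and minimum systolic pressure are captured properly, because the largest of the 8-hour maxima is the largest monitored value. They are still not like-for-like with an infant read three times a day, who has fewer chances to show an extreme.

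6. **Weight in the tables.** SAP Section 4 presents results overall and by term and pre-term group. At the planned minimum, one monitored infant carries 1/8 = 12.5% of the overall mean, 1/6 ≈ 16.7% of the pre-term mean, or 1/2 = 50% of the term mean. How many will be monitored is not stated.

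**The case against.** The strongest reply is that recording the worst value in each 8-hour period is a sensible safety choice, that the eCRF or table shells (not among the documents) may already label reading type, and that if no infant is monitored the issue vanishes. All of that stands, and it is why the point is conditional. It does not remove the gap in the SAP text, since the protocol provides for monitored infants in three places.

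It is also fair that the harm is small. There is no hypothesis testing and all data are listed (SAP Section 4). LOS signs, including bradycardia and hypothermia, are rated on every treatment day (Protocol 5.6.5), and adverse events are still reported.

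Four stronger readings are tempting and should not be drawn:

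- **That low-side events go undetected.** The daily LOS ratings and AE reporting remain, so the documents do not support this.
- **That the size of the artefact can be stated** in standard deviations or beats per minute. Any such number would rest on assumed inputs.
- **That observed mean changes will run in the artefact's direction.** Infants enter acutely ill (Protocol 4.2), and recovery also moves these values. The direction in the working is that of the artefact alone.
- **That the SAP 4.3.3 tie-break** ("the latest recorded values will be used in visit summaries") will choose arbitrarily between single readings and extremes. This presumes that both are collected side by side, which the protocol nowhere says. The rule also yields where something else is stated, and SAP 9.4 refers to timepoints within visits.

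**Conclusion.** The point holds as a minor one. For continuously monitored infants, the SAP as written yields on-treatment changes from baseline shifted in a known direction, and opposite-side extremes that cannot be relied on to show the true extreme. Collected-side extremes validly capture the worst value but are not comparable with thrice-daily readings.

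This rests on two conditions: that the extremes fill the three daily recordings, and that the baseline is a single reading. Only the direction is established. The effect is confined to descriptive tables of one component of the primary endpoint. EOT values cannot be assumed free of it, because EOT can fall on the last dosing day and nothing says the value is then a single reading.

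**What to change.** Amend SAP 9.4 and the table shells:

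1. Identify which on-treatment and EOT values are 8-hour extremes, from the eCRF if it records this and otherwise by a one-off site query. Flag them in tables and listings.
2. For those infants report only the collected-side minimum or maximum, labelled 'worst 8-hour value'. Do not tabulate the opposite side as a minimum or maximum.
3. Do not pool 8-hour extremes with single readings in change from baseline. Put them in a separately labelled row, or footnote them as extreme minus single reading. Base like-for-like change on single readings, and include EOT only where the value is confirmed to be one.
4. Record the departure from Protocol 8.4.1.1 in SAP Section 12, which at present declares no changes from the protocol's analyses.

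The cost is wording, shell changes and possibly one query round in a study of about eight infants. The real loss is that monitored infants have no opposite-side extreme, and no on-treatment like-for-like change where single readings do not exist. Splitting rows also makes small groups smaller.

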### **5.5.4 Laboratory parameters and PK sampling**

The local laboratory tests include haematology, blood chemistry and urine analysis (dipstick) parameters as per the schedule of assessments ([Table 3](#)) and [Table 4](#). Additional testing may be performed whenever clinically indicated at the discretion of the Investigator. All samples for a given study site must be analysed by the same local laboratory throughout the study, as designated by the Investigator. The results are to be printed, signed and dated by the Investigator or his/her designee.

In the event of unexplained abnormal laboratory test values, the tests must be repeated and followed up until return to the normal range, stabilisation, and/or until an adequate explanation of the abnormality has been determined. When a clear explanation is established this must be recorded in the eCRF.

